6.5.4.5 Immune Cell-Associated Neurotoxicity Syndrome (ICANS)

Immune cell-associated neurotoxicity syndrome (ICANS) is a neuropsychiatric syndrome which is frequently associated with CRS; however, it is specifically excluded from the definition of CRS and can occur during the course of CRS, after its resolution, or independently from CRS. Clinical findings can be progressive and may include aphasia, altered level of consciousness, impairment of cognitive skills, motor weakness, seizure, and cerebral edema. Severity is evaluated using the ASTCT Consensus grading scale, with ICE score for encephalopathy assessment (Section 10.11 of the master protocol). Recommendations for ICANS management mainly include the use of steroids, whereas tocilizumab, or alternative therapies per site practice in CRS management, should only be used in the context of CRS, as outlined in [Table 7](#). The proposed management should be considered only as recommendations and in light of recommendations from site specialist.

Table 7 - Guidelines for the management of immune Cell-Associated Neurotoxicity Syndrome (ICANS)

Event severity (ASTCT Consensus Grading criteria)	Recommended SAR444245 dose modification and supportive care guidelines
Mild Grade 1 ICE score 7-9. Awakens spontaneously	No intervention required other than close clinical monitoring.
Moderate Grade 2 ICE score 3-6. Awakens to voice.	SAR444245 ^a should be delayed. Treatment with IV corticosteroids should be initiated as needed. SAR444245 may be resumed only after participant recovery or improvement to Grade 1 after corticosteroid taper. Consideration for reduction of SAR444245 dose to █ μg/kg as per Investigator with Sponsor consultation.
Severe or Life-threatening Grade 3 ICE score 0-2. Awakens only to tactile stimulus. Any clinical seizure focal or generalized that resolves rapidly or nonconvulsive seizures on EEG that resolve with intervention.	If Grade 3 ICANS, SAR444245 should be delayed. When symptoms have resolved or improved to Grade 1 after corticosteroid taper, SAR444245 can be either restarted at █ μg/kg or permanently discontinued, as clinically indicated, and upon discussions between the Investigator and Sponsor.
Grade 4 ICE score: 0 (participant isunarousable and unable to perform ICE). Participant isunarousable or requires vigorous or repetitive tactile stimuli to arouse. Stupor or coma. Life-threatening prolonged seizure (>5 min): or Repetitive clinical or electrical seizures without return to baseline in between. Deep focal motor weakness such as hemiparesis or paraparesis. Diffuse cerebral edema on neuroimaging; decerebrate or decorticate posturing; or cranial nerve VI palsy; or papilledema; or Cushing's triad.	If Grade 4 ICANS, SAR444245 should be permanently discontinued. Treatment with IV corticosteroids should be initiated. Concomitant CRS may require tocilizumab, or alternative therapies per site practice in CRS management, and should be handled as described in Table 5 . Corticosteroids can then be administered IV or orally every 8 hours for up to 3 days, then tapered over 4 days. For both Grade 3 and Grade 4 ICANS If there is no clinical improvement within 24 to 72 hours, then re-evaluation for other contributing conditions should be done. Administration of IV Tocilizumab, or alternative therapies per site practice in CRS management, at 8 mg/kg (for participants weighing ≥30 kg, total dose should not exceed 800 mg) should be considered, and steroids should be administered concurrently and repeated as previously mentioned for CRS. Neurologist and other relevant clinical specialists should be involved whenever indicated.

a Information for preparation and storage of SAR444245 is provided in the pharmacy manual

Abbreviations: AE = Adverse event; ASTCT=American Society for Transplantation and Cellular Therapy; CRS= cytokine release syndrome; IV = Intravenous; NCI = National Cancer Institute.

6.5.4.6 Vascular Leak Syndrome (VLS)

Vascular leak syndrome (VLS) is a disorder characterized by leakage of intravascular fluids into the extravascular space and can lead to generalized edema and multiple organ failure. This syndrome is observed in patients who demonstrate a state of generalized leaky capillaries following shock syndromes, low-flow states, ischemia-reperfusion injuries, toxemias, medications, or poisoning. In various human diseases, an increase in capillary permeability to proteins leads to the loss of protein-rich fluid from the intravascular to the interstitial space manifested by any of the following **clinical presentations: diffuse pitting edema, exudative serous cavity effusions, noncardiogenic pulmonary edema, hypotension, and, in some cases, hypovolemic shock with multiple-organ failure**. Fluid management is the cornerstone of VLS management; it is a balance between maintaining the intravascular volume to ensure organ perfusion to prevent organ failure, while avoiding volume overload. The management of VLS according to severity grading is described in [Table 8](#). These guidelines are not comprehensive and the Investigator should exercise clinical judgment based on the symptoms and condition of the individual participant and refer to current guidelines to the topic [\(29\)](#).

Table 8 - Guidelines for the management of Vascular Leak Syndrome (VLS)

Event severity (NCI-CTCAE V5.0)	Recommended SAR444245 dose modification and supportive care guidelines
Mild Grade 1 Asymptomatic	No intervention required other than clinical monitoring.
Moderate Grade 2 Symptomatic; medical intervention indicated	SAR444245 should be delayed. Upon resolution of VLS or improvement to Grade 1, SAR444245 ^a can be resumed at the reduced dose of █ µg/kg. The initial strategy is to administer boluses of crystalloids with a goal of providing the minimum effective volume that optimizes blood pressure together with a fluid-restrictive strategy is advocated to limit interstitial fluid volume expansion.
Severe or Life-threatening Grade 3: Severe symptoms; intervention indicated Grade 4: Life-threatening consequences; urgent intervention indicated	If Grade 3 or Grade 4 VLS, SAR444245 should be permanently discontinued. In participants with severe shock, blood pressure may be only partially responsive or refractory to IV crystalloid fluids. Severe or persistent hypotension is to be managed by the administration of vasopressors. A trial of 25% albumin IV is an additional option, although its efficacy is limited to those with a severe capillary leak. In those who remain with refractory shock in the setting of low filling pressures, high molecular weight starches such as hetastarch (MW 450 kDa) and pentastarch (MW 264 kDa) may be effective in expanding the intravascular volume. Supportive care with invasive and noninvasive ventilation as well as renal replacement may be necessary in severe cases. When available, disease-

Event severity (NCI-CTCAE V5.0)	Recommended SAR444245 dose modification and supportive care guidelines
	
specific therapy should be initiated as soon as possible to facilitate recovery.
 
During the recovery phase from severe capillary leak, the endothelial injury resolves and the capillary leak becomes less important, resulting in stabilization of blood pressure, at which time fluid overload symptoms and signs may predominate (eg, pulmonary edema, pleural effusions, acute respiratory distress syndrome, systemic edema, ascites). Volume removal with loop diuretics is the first-line therapy in these patients. In those with marginal blood pressure and fluid overload, the combination of loop diuretics and 25% albumin IV may facilitate volume removal. Patients with AKI refractory to diuretics will require renal replacement.

a Information for preparation and storage of SAR444245 is provided in the pharmacy manual.

Abbreviations: AE = Adverse event; CTCAE = Common terminology criteria for adverse events; IV = Intravenous; NCI = National Cancer Institute.

6.5.4.7 **Tumor Lysis Syndrome (TLS)**

Tumor lysis laboratory tests (corrected calcium, magnesium, phosphate, uric acid, and lactate dehydrogenase [LDH] levels) will be obtained every 8 hours on C1D1 for safety run-in participants and participants who are hospitalized, and C1D2-D3 for safety run in or participants who are hospitalized because of high tumor burden or at investigator's discretion (refer to [Section 1.3 SOA](#) for details). If it occurs, appropriate treatment will be initiated that will include correction of serum calcium, potassium, or phosphorus abnormalities, and treatment of hyperuricemia with allopurinol and/or rasburicase, as indicated in Appendix 12 of the master protocol ([30](#)).

6.6 CONTINUED ACCESS TO INTERVENTION AFTER THE END OF THE STUDY

Please refer to the master protocol.

6.7 TREATMENT OF OVERDOSE

Please refer to the master protocol for definition and treatment of SAR444245 overdose.

An overdose of pembrolizumab will be defined as any dose of 1000 mg or greater. There is no specific antidote for overdose with pembrolizumab. No specific information is available on the treatment of overdose of pembrolizumab. In the event of overdose, the participant should be observed closely for signs of toxicity. Appropriate supportive treatment should be provided if clinically indicated.

6.8 CONCOMITANT THERAPY

Please refer to the master protocol.

7 DISCONTINUATION OF STUDY INTERVENTION AND PARTICIPANT DISCONTINUATION/WITHDRAWAL

7.1 DISCONTINUATION OF STUDY INTERVENTION

Please refer to the master protocol.

7.2 PARTICIPANT DISCONTINUATION/WITHDRAWAL FROM THE STUDY

Please refer to the master protocol.

7.3 LOST TO FOLLOW UP

Please refer to the master protocol.

8 STUDY ASSESSMENTS AND PROCEDURES

Please refer to the master protocol.

8.1 EFFICACY ASSESSMENTS

Please refer to the master protocol.

8.2 SAFETY ASSESSMENTS

Please refer to the master protocol.

8.3 ADVERSE EVENTS (AES), SERIOUS ADVERSE EVENTS (SAES) AND OTHER SAFETY REPORTING

Please refer to the master protocol.

8.3.1 Time period and frequency for collecting AE and SAE information.

Please refer to the master protocol for AEs and SAEs collection. For participants in Cohort A, irAEs will be collected until 3 months following last administration of study treatment regardless of whether or not another anticancer therapy is initiated.

8.3.2 Method of detecting AEs and SAEs

Please refer to the master protocol.

8.3.3 Follow-up of AEs and SAEs

Please refer to the master protocol.

8.3.4 Regulatory reporting requirements for SAEs

Please refer to the master protocol.

For pembrolizumab, serious adverse events (SAEs) that are considered expected will be specified in the reference safety information (country-approved product labeling for pembrolizumab).

8.3.5 Pregnancy

Please refer to the master protocol.

8.3.6 Cardiovascular and death events

Please refer to the master protocol.

8.3.7 Disease-related events and/or disease-related outcomes not qualifying as AEs or SAEs

Not applicable.

8.3.8 Adverse event of special interest

Please refer to the master protocol.

In addition, symptomatic or asymptomatic overdose with pembrolizumab are described as below:

- An overdose of pembrolizumab will be defined as any dose of 1000 mg or greater.

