8.3.8 Adverse event of special interest

Adverse event of special interest

An AESI is an AE (serious or nonserious) of scientific and medical concern specific to the Sponsor's product or program, for which ongoing monitoring and immediate notification by the Investigator to the Sponsor is required. Such events may require further investigation in order to characterize and understand them. Adverse events of special interest may be added, modified or removed during a study by protocol amendment. The following events need to be reported as AESIs:

- Pregnancy of a female participant entered in a study as well as pregnancy occurring in a female partner of a male participant entered in a study with IMP/NIMP
 - Pregnancy occurring in a female participant entered in the clinical trial or in a female partner of a male participant entered in the clinical trial. It will be qualified as an SAE only if it fulfills one of the seriousness criteria (see Appendix 3 [[Section 10.3](#)]).
 - In the event of pregnancy in a female participant, IMP should be discontinued.
 - Follow-up of the pregnancy in a female participant or in a female partner of a male participant is mandatory until the outcome has been determined (See Appendix 4 [[Section 10.4](#)]).
- Symptomatic overdose (serious or nonserious) with IMP/NIMP
 - An overdose of IMP is defined as: increase of at least 30% of the dose to be administered in the specified duration or if the dose is administered in less than half the recommended duration of administration.
 - An overdose (accidental or intentional) with the NIMP is an event suspected by the Investigator or spontaneously notified by the participant (not based on systematic pills count) and defined as at least twice the intended dose within the intended therapeutic interval, adjusted according to the tested drug.
- An elevated AST or ALT lab value that is greater than or equal to 3X the ULN and an elevated total bilirubin lab value that is greater than or equal to 2X the ULN and, at the same time, an alkaline phosphatase lab value that is less than 2X the ULN, as determined by way of protocol-specified laboratory testing or unscheduled laboratory testing*.

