Additionally, pharmacology data clearly show target saturation at 200 mg Q3W. First, PK data in KN001 evaluating target-mediated drug disposition (TMDD) conclusively demonstrated saturation of PD1 in systemic circulation at doses much lower than 200 mg Q3W. Second, a PBPK analysis was conducted to predict tumor PD1 saturation over a wide range of tumor

penetration and PD1 expression. This evaluation concluded that pembrolizumab at 200 mg Q3W achieves full PD1 saturation in both blood and tumor.

Finally, population PK analysis of pembrolizumab, which characterized the influence of body weight and other participant covariates on exposure, has shown that the fixed-dosing provides similar control of PK variability as weight-based dosing, with considerable overlap in the distribution of exposures from the 200 mg Q3W fixed dose and 2 mg/kg Q3W dose. Supported by these PK characteristics and given that fixed-dose has advantages of reduced dosing complexity and reduced potential of dosing errors, the 200 mg Q3W fixed-dose was selected for evaluation across all pembrolizumab protocols.

To date, pembrolizumab (2 mg/kg Q3W) has been evaluated in 161 pediatric participants (aged 1 to 18 years) with advanced melanoma, PD-L1 positive advanced, relapsed, or refractory solid tumors, or lymphoma. The exposures in pediatric participants following the 2 mg/kg Q3W regimen were found to be similar to that observed in adult participants. Pediatric data has also been incorporated in an integrated population PK analysis, which confirmed that a pembrolizumab dose of 2 mg/kg Q3W (up to a maximum of 200 mg Q3W) in pediatric participants renders exposures similar to adults. Based on these results, the pediatric dose for evaluation in this trial is 2 mg/kg Q3W (up to a maximum of 200 mg Q3W).

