6.1.1 Investigational medicinal product

Investigational medicinal product (IMP) is defined as SAR444245, and pembrolizumab administered as described in [Section 4.1](#). Details of each IMP component to be administered are shown in [Table 2](#).

Preparation and administration of IMP are detailed in the pharmacy manual. Hydration is required for SAR444245 infusions. Details are provided in Section 6.1.3 of the master protocol.

Table 2 - Overview of IMP administered

Intervention name	SAR444245	Pembrolizumab
Type	See master protocol	Biologic
Dose formulation	See master protocol	Solution for infusion
Unit dose strength(s)	See master protocol	100 mg/vial
Dosage level(s)^a	24 µg/kg Q3W (or reduced to █ µg/kg █ or another lower dose level recommended by Study Board)	200 mg Q3W (for pediatric participants: 2 mg/kg, up to maximum 200 mg)
Route of administration	See master protocol	IV infusion
Use	See master protocol	Treatment of cancer (combination)
IMP or NIMP	IMP	IMP
Packaging and labeling	See master protocol	Supplied in single-dose vials containing 100 mg/4 mL pembrolizumab labelled with a multilingual booklet. 1 vial per treatment box.
Current/Former name(s) or alias(es)	NA	Keytruda

^a The total dose will be calculated based on the weight on the day of the infusion or the most recent weight assuming it was assessed in a reasonable time frame according to Investigator assessment. Study sites should make every effort to measure body weight as close to the infusion day as possible considering the variability of local process from site to site. If the infusion is prepared with the most recent weight assessed in a reasonable time frame, the participant must still be weighed on D1 of each cycle, and the weight recorded in the electronic case report form (e-CRF). Study sites should make every effort to target infusion timing to be as close to 30 minutes as possible. However, given the variability of infusion pumps from site to site, a window between -5 minutes and +10 minutes is permitted (ie, infusion time is 30 minutes -5 min/+10 min).

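### Substudy 01 fixes pembrolizumab overdose at 1000 mg for everyone, so the trigger is 5 times the planned dose in adults but 10 times or more in adolescents of 50 kg or less

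*Protocol*

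**What the plan says.** Substudy 01 treats pembrolizumab as a study drug: "Investigational medicinal product (IMP) is defined as SAR444245, and pembrolizumab" (section 6.1.1). Table 2 there gives 200 mg every 3 weeks for adults and 2 mg/kg, at most 200 mg, for pediatric participants. Master protocol 5.1 admits participants from age 12 and sets no weight criterion.

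On overdose, Substudy 01 gives the same fixed limit in 6.7 and 8.3.8: "An overdose of pembrolizumab will be defined as any dose of 1000 mg or greater". Neither section has a pediatric or weight-based version. Section 8.3.8 first refers to the master protocol and then introduces the limit with "In addition, symptomatic or asymptomatic overdose with pembrolizumab are described as below". Section 6.7 borrows from the master protocol for the other drug only: "Please refer to the master protocol for definition and treatment of SAR444245 overdose". For pembrolizumab it says: "In the event of overdose, the participant should be observed closely for signs of toxicity".

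The AESI list in master protocol 8.3.8 has the entry "Symptomatic overdose (serious or nonserious) with IMP/NIMP", and under it: "An overdose of IMP is defined as: increase of at least 30% of the dose to be administered in the specified duration". That entry says nothing about overdose without symptoms.

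**The concern.** The dose scales with weight in pediatric participants, but the overdose trigger does not. The sponsor chose to make pembrolizumab overdose without symptoms an AESI. In a light adolescent that provision starts only at a far larger multiple of the planned dose than in an adult.

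At stake is prompt notice. An AESI goes to the sponsor within 24 hours (master protocol 8.3.1) and enters the SAP's AESI table, which is selected by the eCRF tick box (SAP 3.6.2). An asymptomatic pediatric overdose below 1000 mg does neither. It is also unclear whether the immediate sponsor contact in master protocol 6.7, or the close observation in Substudy 01 6.7, applies below 1000 mg, because both depend on which overdose definition governs.

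**Working it through.** **Inputs.** Overdose limit 1000 mg (Substudy 01, 6.7 and 8.3.8). Planned dose 200 mg in adults, and min(200, 2 × kg) mg in pediatric participants (Substudy 01, Table 2). Master 30% rule (master protocol 8.3.8). The documents give no adolescent weights, so 30, 40 and 50 kg are assumptions. The 100 kg row is where the pediatric dose reaches its cap.

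**The plan's own figure.** No derivation of 1000 mg is given. Its ratio to the adult dose is 1000 / 200 = 5.

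**Pediatric ratio.** Below 100 kg, 1000 / (2 × kg) = 500 / kg. The 30% rule gives 1.3 × 2 × kg = 2.6 × kg mg. Five times the planned dose is 10 × kg mg.

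| Weight (kg) | Planned (mg) | 1000 mg as multiple of planned | 30% rule (mg) | 5 times planned (mg) |
|---|---|---|---|---|
| 30 | 60 | 16.7 | 78 | 300 |
| 40 | 80 | 12.5 | 104 | 400 |
| 50 | 100 | 10 | 130 | 500 |
| 100 | 200 | 5 | 260 | 1000 |

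**Is there another route to AESI status?** Two readings are possible.

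- *The substudy adds to the master list.* Pembrolizumab is an IMP, so a symptomatic overdose is an AESI from 1.3 times the planned dose. An asymptomatic one is an AESI only from 1000 mg, because the 30% rule sits under the symptomatic entry.
- *The master definition is for SAR444245 only, as Substudy 01 6.7 suggests.* Then 1000 mg is the only pembrolizumab limit, with or without symptoms.

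The readings differ for symptomatic overdose. They agree that an asymptomatic one below 1000 mg is not an AESI.

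**Smaller errors.** A whole 100 mg vial is 100/60 = 1.67 times planned at 30 kg and 100/80 = 1.25 times at 40 kg. The flat adult 200 mg is 200/60 = 3.3, 200/80 = 2.5 and 200/100 = 2.0 times planned at 30, 40 and 50 kg. All are below 5 times.

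**The case against.** The strongest reply is that this is a deliberate and fairly strict sponsor choice. Under the master protocol an asymptomatic overdose of SAR444245 of any size is not an AESI, so Substudy 01 goes further by adding asymptomatic pembrolizumab overdose at all. Nor is the gap only pediatric: an asymptomatic adult dose above 200 and below 1000 mg is equally unflagged. This stands. What is specific to adolescents is the size of the multiple.

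A reader might infer that tenfold pediatric errors would pass unnoticed. The arithmetic allows part of this: a tenfold error is 20 mg/kg, which is below 1000 mg for anyone under 50 kg. But the documents make such an error unlikely. Vials hold 100 mg and come one per box (Substudy 01, Table 2), so at 30 or 40 kg one vial suffices, and a tenfold dose of 600 or 800 mg needs 6 or 8. A second staff member confirms each dose (master protocol 6.4).

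Nor does failing to be an AESI mean going unrecorded. Doses and changes to administration are recorded in the e-CRF (master protocol 6.4; Substudy 01, 6.5.1). Sequelae of a suspected overdose are AEs (master protocol 10.3.1), and the event-based AESIs still apply. The SAP summarises pembrolizumab dose and relative dose intensity (3.6.1.3) and critical and major protocol deviations (Appendix 2).

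The 10 mg/kg figure has no stated safety basis. Substudy 01 4.3.2 mentions 10 mg/kg as a comparison dose in melanoma and lung cancer trials, but the flat relationship it reports concerns efficacy, and the pediatric experience it cites is at 2 mg/kg. A ratio to planned dose also treats equal weights unequally: at 50 kg, a 17-year-old would be flagged at 500 mg and an 18-year-old at 1000 mg. Both objections stand as limits on the fix.

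**Conclusion.** The point holds as an optional improvement. The fixed limit is 5 times the planned dose in adults and 500/kg times in pediatric participants below 100 kg, and no provision makes an asymptomatic pediatric overdose below that limit an AESI. The formula is exact; the multiples of 16.7, 12.5 and 10 rest on the assumed weights. Pediatric is read here as age 12 to under 18.

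The practical consequence is small. It needs a light adolescent among about 25 participants, at a site outside France (where only adults enrol), a gross dosing error, and no symptoms. The documents do not say how many adolescents are expected. What is lost is a prompt formal report, not the record of the dose. The documents do not support saying that symptomatic pediatric overdoses are also missed: that depends on an unsettled reading, and on one reading they are caught from 2.6 mg/kg. Efficacy analyses, sample size and dose decisions are untouched.

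**What to change.** In Substudy 01, sections 6.7 and 8.3.8, keep the 1000 mg rule and add: *in pediatric participants, any dose of at least 5 times the planned dose (10 mg/kg) or 1000 mg, whichever is lower*. Leave the master protocol's definition alone, so that any existing 30% trigger for symptomatic overdose is kept.

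The sponsor should know that the 5-times ratio is only inferred from 1000/200 mg; the documents state none. The clause will not catch smaller and likelier errors, such as a whole 100 mg vial or the flat 200 mg dose.

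The cost is one clause in two sections at the next amendment, at most a few extra AESI reports, and different thresholds for an adolescent and an adult of the same weight.
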